### **Primary Analysis:**

Our primary hypothesis is that by providing anti-SARS-CoV-2 plasma, the cumulative incidence of the development of active infection will be lower among the individuals receiving HCIP as compared to those receiving control plasma over the course of follow-up. Therefore, our primary endpoint is the development of COVID-19 within the follow-up period. For clarity the working definition of our endpoint is positive for SARS-CoV-2 by molecular test with or without any symptoms compatible with COVID-19. To allow to differentiate between all infections and asymptomatic infections, the analyses will be done using 1) all infections as indicated by research based RT-PCR or capture of positivity by clinical testing and then again for 2) symptomatic infection based upon symptoms compatible with COVID-19 infection and being positive by molecular test (research sample or clinical result). For the primary analysis, individuals who test positive by a molecular test on the calendar day of transfusion will be excluded from the analysis. Individuals whose specimens obtained at screening visit who test positive on two antibody tests done by [name] laboratory using the Euroimmune assay and [name] using antibody ELISA end point titer and area under curve, will be excluded as indication of a prior unknown COVID-19 infection.

Our analysis will be a time to event analysis examining the effect of anti-SARS-CoV-2 plasma. We will estimate the survival function for each treatment arm in order to estimate the risk difference over time as well as the restricted mean survival time which is the area under the survival function and provides the expected mean time to infection up to time  $t^2$ . Our approach will be to estimate the cumulative incidence using the doubly robust estimator based upon targeted minimum loss (TMLE) based estimator as described by Diaz et al (2019). By adjusting for baseline covariates that are related to the outcome, we increase precision. This TMLE based approach was shown to increase precision by around 10% to 20% over an inverse probability weighted or augmented inverse probability weighted estimator [Diaz 2019]. As stated above, we will use a hybrid approach of adjusting for pre-specified variables (age) and an algorithmic approach to identify additional variables related to the outcome. Specifically, a random survival forest will be used to identify variables that are related to the outcome in order to increase precision. We will use a random survival forest blinded to the treatment arm allocation and *not* including an indicator variable for treatment (pre-randomization variables to be considered are listed above).

The primary outcome analysis will be the adjusted comparison of proportions of cumulative incidence of SARS-CoV-2 infection (as indicated by RT-PCR positive) at day 28 comparing the risk-difference and restricted mean survival time between treatment groups with confidence intervals and using a significance threshold of  $p=0.047$  (p-value adjusted for interim analysis) for a one-sided test. This will be repeated for analysis of the cumulative incidence of SARS-CoV-2 symptomatic disease as defined as having a confirmed SARS-CoV-2 positive test and at least one symptom including new/incident: fever, cough, sore throat, malaise, headache, muscle pain, nausea, vomiting, loss of taste, loss of smell, shortness of breath, or dyspnea as per the FDA recommendations in Appendix A within "COVID-19: Developing Drugs and Biological Products for Treatment or Prevention: Guidance for

Industry [<https://www.fda.gov/media/137926/download>]. Therefore, we will be assessing both the effect of convalescent plasma on overall infection including asymptomatic disease and its effect on symptomatic disease.

Additional sensitivity analysis include:

1. A per-protocol analysis that accounts for those who received a transfusion and were not transfused with their specific treatment group (i.e., non-adherence) using inverse probability weights to account for non-adherence.
2. Classifying participants with missing outcome data at either day 14 or day 28 as having developed COVID-19 with date of COVID-19 being drawn from distribution reflecting the corresponding treatment arms;
3. Multiple imputation of the development of COVID-19 for missing outcomes;
4. A complete case analysis;
5. As convalescent plasma is unlikely to have an immediate effect after transfusion, we will exclude any events occurring between transfusion and 3 calendar days afterwards;
6. As symptoms compatible with COVID-19 may be non-specific and increase false positives, we had elected to use molecular test with or without COVID-19 symptoms as our outcome for any infection and positive test with at least 1 symptom compatible with COVID-19 to define symptomatic infection. As a sensitivity analysis we will conduct a series of analyses that iteratively increases the number of symptoms compatible with COVID-19 required to be present to define symptomatic COVID-19 infection (e.g.,  $\geq 2$ ,  $\geq 3$ , ...). Any individuals who have a pre-existing symptom (perhaps due to prior co-morbidity) that maximizes the number of incident symptoms will be considered positive for any of the sensitivity analyses that are above what they can have. .

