4.3.2. Exclusion Criteria for Enrollment

1. Medical, psychiatric, or cognitive illness or recreational drug/alcohol use that in the opinion of the principal investigator, would affect subject safety and/or compliance
2. Symptoms consistent with COVID-19 infection at time of screening (sudden onset of at least one of the following: fever, cough, shortness of breath)
3. Laboratory evidence of COVID-19 infection at time of screening
4. History or known laboratory evidence of previous COVID-19 infection
5. A history of or known prior allergic reaction to transfusion blood product
6. Receipt of SARS-CoV-2 Vaccine

Table: Schedule of Events

Study period	Screen	Baseline	Transfusion	Follow up						
				1	3	7	14	28	60	90
Day	-1 to 0	0	0							
Window				+/- 1 day	+/- 1 day	+/- 1 day	+/- 3 days	+/- 3 days	+/- 3 days	+/- 8 days
Eligibility										
Informed consent	x									
Demographic and Medical history	x									
COVID-19 symptom survey	x									
SARS-CoV-2 molecular testing for eligibility	x									
Pregnancy test ⁴	x									
ABO ⁵	x									
Study Drug Administration										
Randomization		x								
Drug infusion			x							
Study Procedures										
Vital signs	x	x	xxxx ⁶	x		x	x			
Physical examination			x							
COVID-19 symptom screen	x	x	x	x	x	x	x	x	x	
Concomitant medications	x	x	x							
Assessment of clinical event scale of disease severity ⁷		x		x	x	x	x	x	x	
Adverse event monitoring		x	x	x	x	x	x	x	x	

⁴ Result of urine or serum pregnancy test for women of childbearing potential must be documented prior to transfusion

⁵ Assessment of ABO type on file or determination of ABO type if not on file

⁶ Vital sign testing: Immediately prior to infusion, 10-20 minutes after start of infusion, at completion of infusion and 30-60 minutes after the end of the infusion

⁷ Assessment evaluates whether subject has shifted from “no clinical or laboratory evidence of COVID-19 infection to any of the clinical event scale of disease severity

Laboratory testing										
CBC and CMP	x			x		x	x			
SARS-CoV-2 molecular testing ⁸	x			x		x	x	x		
Blood for future testing ⁹	x			x		x	x			x

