## **Power and Sample Size**

We hypothesize that outpatient adults with recent exposure to COVID-19 who receive HCIP will have a lower incidence of developing a SARS-CoV-2 infection with COVID-19 when compared with similar adults receiving control plasma. A sample size of 500 individuals with a high risk exposure within 96 hours of enrollment with a 1:1 allocation ratio to each treatment group will have 80% power to detect a 50% reduction in cumulative incidence by 28 days. This is with a one-sided type 1 error of 5% as we are solely interested in superiority. We assumed that the probability of incident COVID-19 cases is between 0.10 and 0.20 in the control population. We explored several different scenarios with an exponential model to identify the lambda parameter and the package 'powerSurvEpi' for the R statistical software was then used to calculate the sample sizes for these scenarios (See Table1). We assumed that the cumulative incidence of symptomatic disease in SARS-CoV-2 exposed individuals randomized to control plasma to be 0.13X by day 28 and 0.065 (50% reduction in risk) by day 28 among those randomized to HCIP. We therefore estimated 488 participants (244 in each arm). It is

---

\*with surge of infections in December 2020 and hospitals becoming more full, these two were put into the clinical events scale as hospitalization equivalents

anticipated that very few of these subjects will be randomized and not start study plasma infusion (and so be excluded from the primary analysis). Furthermore, it is anticipated that there will be low loss to follow-up prior to development of disease or 28 days (and so have missing data for the primary endpoint). Therefore, we have extended the total sample size to 500 participants. For all analyses, we will use a modified intention-to-treat analyses, which excludes randomized subjects who do not initiate an infusion of the study plasma.

Table 1: Total sample size by the incident proportion of COVID-19 among controls and by percent risk reduction

Proportion of Incident COVID-19 cases at day 28 among controls	50% Risk Reduction	75% Risk Reduction
0.10	648	199
0.13	488	150
0.15	415	129
0.20	298	94

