## Statistical Principles

General principles for analysis include the following:

- The primary analysis will be performed according to the participants' original randomized treatment groups excluding those who do not initiate transfusion of study plasma (modified intention to treat).
- All participants, including those who have withdrawn from the study or were found to be ineligible after randomization, will be included in their assigned treatment group and analyzed for safety.
- All outcomes, including death, following randomization will be included. Death in the absence of known infection will be presumed to be indicative of infection.
- Missing data will be minimized by study design and conduct. It will be addressed analytically using multiple imputation methods

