## Secondary Analyses:

A secondary hypothesis is that individuals receiving anti-SARS-CoV-2 convalescent plasma are likely to have less disease severity than control. We have devised a clinical event scale for disease severity based on the COVID clinical severity scale which is composed of clinical events that range from being not infected to death. The event scale is as follows:

1. Death
2. Requiring mechanical ventilation and/or in ICU
3. non-ICU hospitalization, requiring supplemental oxygen;
4. non-ICU hospitalization, not requiring supplemental oxygen  
or  
a stay of >24 hours for observation in an ED, field hospital, or other healthcare unit\*  
or  
any receipt of O2 for >24 hours, outside of hospital\*
5. Not hospitalized, but with clinical and laboratory evidence of COVID-19 infection (symptomatic infection)

---

 Positive molecular testing for SARS-CoV-2

\*with surge of infections in December 2020 and hospitals becoming more full, these two were put into the clinical events scale as hospitalization equivalents

6. Not hospitalized, no clinical symptoms compatible with COVID-19, but with laboratory evidence of COVID-19 infection (asymptomatic infection)
7. No symptoms compatible with infection, no laboratory evidence of COVID-19 (No indication of infection)

This analysis will be done using the status of participants by day 32 (corresponding to day 28 visit allowing for window around the scheduled visit) using a doubly robust estimators for ordinal outcomes and adjusted for the pre-specified candidate variables selected via the algorithm as described above. The doubly robust estimator that will be used is that as outlined by Benkeser et al. (2020) based upon a non-parametric extension of the log-odds ratio by Diaz et al. (2016). A sensitivity analysis will be done in which participants who have indication of positive infection (e.g. clinical scale event <7) at  $\leq 3$  days after transfusion.

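### People PCR-positive on the day of transfusion are excluded from the primary analysis only, so the severity and PCR-positivity analyses can count infections the SAP treats as present before plasma

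*SAP*

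**What the plan says.** The SAP gives its general analysis set under Power and Sample Size: "For all analyses, we will use a modified intention-to-treat analyses, which excludes randomized subjects who do not initiate an infusion of the study plasma". Statistical Principles repeats that set for the primary analysis.

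The Primary Analysis section then adds two exclusions. The first carries an explicit scope: "For the primary analysis, individuals who test positive by a molecular test on the calendar day of transfusion will be excluded from the analysis". The second removes people whose screening specimen is positive on two antibody tests; they "will be excluded as indication of a prior unknown COVID-19 infection". That sentence has no scope phrase of its own and is tied to the primary analysis only by its heading.

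The Secondary Analyses section describes a seven-level ordinal severity analysis: "This analysis will be done using the status of participants by day 32". It states no entry exclusion. Level 6 reads: "Not hospitalized, no clinical symptoms compatible with COVID-19, but with laboratory evidence of COVID-19 infection (asymptomatic infection". The section ends with a sentence beginning "A sensitivity analysis will be done in which participants who have indication of positive infection", which limits the group to positives at 3 days or less after transfusion and stops without saying what is done with them.

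Under Other Analyses, the PCR-positivity analysis lists day 0 among its visits and fits a pooled complementary log-log model to obtain a cumulative incidence of positivity. It also states no entry exclusion.

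**The concern.** The sponsor judged that a positive molecular test on the day of transfusion should not count against the plasma, and wrote a rule to that effect. The rule reaches one analysis. Elsewhere the same person is an outcome: level 6 if symptom-free, a worse level otherwise, and a possible event in the cumulative incidence of positivity.

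Such cases are foreseeable. Protocol 4.3.4 requires a negative validated test in the 24 hours before infusion, but Protocol section 6 says study samples go to a central laboratory whose results are not returned in real time. A positive can therefore come to light after infusion.

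Two things are at stake. Infections already present cannot be prevented by plasma, so counting them weakens the infected/uninfected contrast. The primary and secondary results would also describe different sets of people with no stated reason. A reader who assumes the exclusions carry over would build a different secondary set from one who follows the text, and the SAP does not settle which is meant.

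**Working it through.** **Setting the passages side by side**

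| Analysis (SAP section) | Infusion not started | Molecular-positive on transfusion day | Positive on both screening antibody tests |
|---|---|---|---|
| Primary (Primary Analysis) | removed | removed, expressly | removed |
| Ordinal severity (Secondary Analyses) | removed | nothing stated | unclear |
| PCR positivity (Other Analyses) | removed | nothing stated; day 0 is a visit | unclear |

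No section carries the primary exclusions forward, and none says outright that these people stay in. The literal reading is that day-of-transfusion positives stay in.

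**Inputs**

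- From SAP Power and Sample Size: 13% (control) and 6.5% (HCIP) by day 28, one-sided 5%, 80% power, 500 randomized 1:1 (250 per arm).
- Assumed: a fraction b of each arm is already PCR-positive at entry, equal by arm, at 1%, 3% or 5%. The documents give no value.
- Assumed: the planned rates, which the SAP states for symptomatic disease, stand in for any infection among the remainder.

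**The plan's own figure**

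Hazard ratio = ln(0.935)/ln(0.87) = 0.4826. Events = 4(1.645 + 0.842)²/(ln 0.4826)² = 46.6. Total = 46.6/0.0975 = 478, against the stated 488 (2.1% lower). The inputs are therefore read as the plan intends. The sample size is not in dispute here.

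**Effect on the infected/uninfected cut**

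Control: c = b + (1 − b) × 0.13. HCIP: t = b + (1 − b) × 0.065. Share of counted infections present at entry = 2b/(c + t).

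Power = Φ{[(c − t) − 1.645 √(2p(1 − p)/n)] / √[(c(1 − c) + t(1 − t))/n]}, with p = (c + t)/2. If these people are kept, n = 250 per arm. If they are excluded, n = 250(1 − b) per arm at 13% vs 6.5%.

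| b | c | t | Risk ratio | Odds ratio | Share present at entry | Power, kept | Power, excluded |
|---|---|---|---|---|---|---|---|
| 0 | 0.1300 | 0.0650 | 0.50 | 0.47 | 0% | 0.791 | 0.791 |
| 1% | 0.1387 | 0.07435 | 0.54 | 0.50 | 9% | 0.755 | 0.787 |
| 3% | 0.1561 | 0.09305 | 0.60 | 0.55 | 24% | 0.689 | 0.780 |
| 5% | 0.1735 | 0.11175 | 0.64 | 0.60 | 35% | 0.630 | 0.773 |

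The last column shows that most of the loss comes from dilution, not from numbers: removing 5% (25 of 500) lowers power only from 0.791 to 0.773. The absolute difference hardly moves, since it shrinks by the factor 1 − b (6.5 to 6.2 percentage points at 5%). The ratio and odds scales move more, and the secondary estimator is a log-odds type.

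**Seropositives**

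If a fraction of 5% is seropositive, PCR-negative and at no further risk, the rates become 0.95 × 0.13 = 0.1235 and 0.95 × 0.065 = 0.06175. The risk ratio stays at 0.50, and power is 0.771 kept against 0.773 excluded.

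**The case against.** Several counter-arguments have force.

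**The general rule is not exhaustive.** It is worded for all analyses, yet the primary analysis adds to it. Statistical Principles says people who "were found to be ineligible after randomization, will be included in their assigned treatment group and analyzed for safety", which is compatible with removing them from efficacy analyses generally. This leaves room for an intention to carry the exclusions over. It does not put that intention in the text, and the molecular rule is expressly limited.

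**These people need not be ineligible.** A reader might infer that the secondary population contains people who breach the protocol's exclusions. The documents do not support that. Exclusion 3 in Protocol 4.3.2 reads "Laboratory evidence of COVID-19 infection at time of screening", and a later positive on the transfusion day need not breach it. Exclusion 4 covers a history or known evidence of infection, whereas the SAP describes the antibody-detected cases as unknown. The sound description is narrower: people the SAP itself treats as infected before plasma.

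**Severity is a different question.** Plasma might still modify illness in someone already infected, so keeping all infused participants in a severity analysis is defensible; Protocol 5.2.2 even restricts that analysis to infected people. This stands. Dilution is therefore shown only for the infected/uninfected part of the scale, and an all-infused analysis deserves a place.

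**The PCR analysis is mainly descriptive.** Reporting Day 0 positivity there looks deliberate. The difficulty is only that a cumulative incidence is built from the same visits.

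**Early positives have a sensitivity analysis.** It would cover Day 0, but it leaves the main secondary analysis unchanged, does not address seropositives, and lacks a statement of what is done.

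**The arithmetic is not the planned analysis.** Agreed. It is a binary cut with symptomatic-disease rates and a one-sided 5% test, whereas the secondary uses a doubly robust ordinal estimator with no stated alpha or power.

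**Conclusion.** The point holds for the molecular exclusion. Read literally, day-of-transfusion positives are out of the primary analysis, in the severity analysis at level 6 or worse, and able to enter the cumulative incidence of positivity. For the antibody exclusion the SAP is unclear, not expressly primary-only, and little turns on it numerically.

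On the binary cut, the risk ratio moves from 0.50 to 0.54, 0.60 and 0.64 at assumed prevalences of 1%, 3% and 5%. This rests on equal prevalence by arm and on the planned rates applying to everyone else. It shows scale only and is not the power of the ordinal analysis.

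A reader might also infer a bias in favour of HCIP, or a separate gap in the interim analyses. Neither is supported: with similar prevalence by arm the effect on this cut is towards no difference, and the interim reviews concern the primary outcome. The matter should be settled in the SAP wording; it does not undermine the primary result.

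**What to change.** 1. Define the entry exclusions once: molecular-positive on a sample taken before infusion starts, and positive on both screening antibody assays. Tying the first to the sample time matters because the Day 1 visit window (plus or minus 1 day) lets a post-infusion swab fall on the calendar day of transfusion.
2. Apply them to the main ordinal analysis under Secondary Analyses and to the cumulative-incidence model under Other Analyses, as in the primary analysis.
3. Report Day 0 positivity descriptively only.
4. Keep the all-infused set for safety and as a sensitivity analysis for severity, since plasma might modify severity in those already infected.
5. Complete the sentence on positives at 3 days or less, saying whether these people are removed or reclassified.

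The exclusions rest on entry samples and can be applied blind to arm. The cost is SAP wording and slightly fewer participants in the secondary analyses; no new data are needed.

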**Convalescent Plasma to Stem Coronavirus: A Randomized
Controlled Double Blinded Phase 2 Study Comparing the
Efficacy and Safety of Human Coronavirus Immune Plasma
(HCIP) vs. Control (SARS-CoV-2 non-immune plasma) among
Adults Exposed to COVID-19**

NCT 04323800

Protocol

Version December 23, 2020

1. PROTOCOL SUMMARY:

Long title: Convalescent Plasma to Stem Coronavirus: A Randomized Controlled Double Blinded Phase 2 Study Comparing the Efficacy and Safety of Human Coronavirus Immune Plasma (HCIP) vs. control (SARS-CoV-2 non-immune plasma) among Adults Exposed to COVID-19

Short title: CSSC-001

Clinical Phase: 2

IND Sponsor: Johns Hopkins University

Conducted by: Johns Hopkins University as lead institution for a consortium of sites

Sample Size: 500

Study Population: High-risk subjects aged 18 years of age and older who have experienced a close contact exposure to a person with COVID-19 in the past 120 hours AND have not yet themselves developed symptoms of COVID-19

Study Duration: April 1, 2020 to December 31, 2022

Study Design: This randomized, controlled, double-blinded phase 2 trial will assess the efficacy and safety of Anti- SARS-CoV-2 convalescent plasma as prophylaxis following exposure to COVID-19 (as defined in the inclusion criteria). Adults 18 years of age and older with high risk exposure as defined by CDC may participate. A total of 500 eligible subjects will be randomized in a 1:1 ratio to receive either high titer anti-SARS-CoV-2 plasma or control (SARS-CoV-2 non-immune plasma).

The following will be assessed in all subjects:

- Safety and efficacy: Day 0 (baseline), 1, 3, 7, 14, 28, 60 and 90. May be performed by telemedicine on days when laboratory testing not scheduled.
- Blood antibody titer¹ to SARS-CoV-2s: Day -1 to 0, 1, 7, 14 and 90
- SARS-CoV-2 molecular testing from nasopharyngeal swab, throat samples: Day -1 to 0, 1,7, 14 and 28 and at any time when there is clinical suspicion for COVID-19

Study Agent:

- SARS-CoV-2 convalescent plasma (1 unit; minimum of 175 mL collected by pheresis from a volunteer who recovered from COVID-19 disease and has SARS-CoV-2 antibody titers \geq 1:320
- Control plasma: Plasma collected from a volunteer donor prior to January 1, 2020 will not be tested for SARS-CoV-2 antibodies. Plasma collected after December 31, 2019 will be confirmed as SARS-CoV-2 seronegative.

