4.3.4. Intervention

- I. Subjects will be randomized in a 1:1 ratio to receive treatment vs SARS-CoV-2 non-immune plasma
- II. Study drug: The investigational product is anti-SARS-CoV-2 convalescent plasma. Patients identified as having recovered from COVID-19 will serve as potential donors. Donors with SARS-CoV-2 antibody titers $\geq 1:320$ by validated ELISA will be used for the trial. The ELISA testing will be performed in a CLIA certified laboratory. Potential donors and samples will be screened for transfusion-transmitted infections (e.g. HIV, HBV, HCV, WNV, HTLV-I/II, *T. cruzi*, ZIKV) and plasma will be collected using apheresis technology. This is similar to standard blood bank protocols.
- III. Samples of convalescent plasma will be reserved by the blood bank for further testing
- IV. Active arm will receive 1 unit of anti-SARS-CoV-2 plasma with titers $\geq 1:320$)
- V. Control arm will receive 1 unit of SARS-CoV-2 non-immune plasma
- VI. Both active and control drugs will be in standard plasma unit bags, with a study-specific ISBT label.
- VII. For blood that will be collected locally (Johns Hopkins) the source of donor plasma will be as detailed in protocol JHM IRB00248402.
- VIII. all subjects must be negative for active SARS-CoV-2 via a validated molecular test within 24 hours preceding the plasma infusion.

⁸ Sites could include nasopharyngeal, throat

⁹ Includes anti-SARS CoV-2 titers.

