4.3.5. Randomization

- I. Subjects enrolled in the study will be randomized using an interactive web response system (IWRS) to receive study drug vs control at a 1:1 ratio.
- II. Randomization will occur after the result of the initial coronavirus testing is known to be negative.

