Study staff will wear adequate PPE according to local infection control practices. Local sites will follow their institutional guidelines regarding location and infection control for COVID-19 related research. Samples that require transport will be delivered by courier or a member of the research team and triple packaged for travel (e.g. specimen container, leakproof ziplock bag or other container, outer rigid container with marking such as biohazard symbol, medical specimen or diagnostic specimen).

These tests will be processed at a central investigational laboratory and the results of these tests will not be provided to subjects or their treating physicians in real time. Patients who develop signs and symptoms suggestive of COVID-19 will be referred to standard of care coronavirus testing.

The research team may use remote data collection, which may include use of telemedicine in accordance with the [Guidance for Incorporation of Telemedicine into Research with Human Participants](#) to interview and view the participant. (Relying sites may adhere to their own local policies and guidelines for this remote data collection). For residents at nursing facilities, data that is being routinely collected (e.g. vital signs if being done for clinical care purposes or other clinical or medical record information that is collected for clinical care purposes) may be obtained from the nursing facility with appropriate authorization for release.

The testing and specimen collection will be conducted in accordance with the Johns Hopkins HEIC policies for managing patients and with recent COVID exposure, and protection for study staff (mask, PPE when required) as appropriate. The HEIC protocols are:

https://intranet.insidehopkinsmedicine.org/heic/novel_coronavirus/clinical_resources

https://intranet.insidehopkinsmedicine.org/heic/docs/2019-nCoV_outpatient_guidelines.pdf

https://intranet.insidehopkinsmedicine.org/heic/docs/2019-nCoV_patient_discharge_protocol.pdf

Local sites will follow their institutional guidelines regarding infection control and PPE for COVID-19 related research.

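### The only molecular exclusion in the primary analysis is tied to the transfusion date, so a Day -1 research swab read positive later stays in while the same result on a Day 0 swab is removed

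*SAP*

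**What the plan says.** The SAP (Statistical Principles) analyses participants as randomised and leaves out those who never start a transfusion. Its Primary Analysis section adds two exclusions. The molecular one is that "individuals who test positive by a molecular test on the calendar day of transfusion will be excluded from the analysis". The serological one covers screening specimens positive on two antibody assays, which "will be excluded as indication of a prior unknown COVID-19 infection". The primary endpoint is any molecular positive, with or without symptoms.

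The entry rules come first:

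- Protocol 4.3.2 excludes "Laboratory evidence of COVID-19 infection at time of screening".
- Protocol 4.3.5 states that "Randomization will occur after the result of the initial coronavirus testing is known to be negative".
- Protocol 4.3.4 requires that "all subjects must be negative for active SARS-CoV-2 via a validated molecular test within 24 hours preceding the plasma infusion". Section 6 repeats this in its text on infusion sites.

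On sampling, the protocol summary lists "SARS-CoV-2 molecular testing from nasopharyngeal swab, throat samples: Day -1 to 0, 1,7, 14 and 28". The Schedule of Events (4.3.2) has two molecular rows at screening, one for eligibility and one in the laboratory block. On processing, section 6 states: "These tests will be processed at a central investigational laboratory". On reporting back, the same sentence adds that "the results of these tests will not be provided to subjects or their treating physicians in real time".

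**The concern.** The molecular exclusion only has work to do if some transfused participants turn out to have been positive at baseline despite the entry rules. The sponsor has thus already decided that such people do not belong in the primary analysis, but the wording reaches only some of them. Screening and transfusion can fall on different dates: the pre-dose swab has a Day -1 to 0 window, and protocol 4.5 allows up to 24 hours between randomisation and infusion. Whether a baseline positive is removed then depends on whether the two shared a calendar day. The adjacent antibody exclusion is anchored to the screening visit, so two neighbouring rules use different reference points.

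An infection present before transfusion cannot be prevented by the plasma. Counted as an event, it adds equally to both arms in expectation and carries no information about the treatment effect.

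**Working it through.** **Which participants are affected.** Four conditions must hold together:

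1. The eligibility test was negative (otherwise protocol 4.3.2, 4.3.4 and 4.3.5 keep the person out).
2. A separate research specimen was collected on Day -1, and transfusion was on Day 0.
3. That specimen was read positive only afterwards.
4. The person was not positive on both antibody tests at screening.

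The SAP's molecular rule does not reach this person, and the modified intention-to-treat rule removes only those not transfused. With a Day 0 specimen and everything else equal, the person is excluded.

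**Reproducing the plan's sample size.** Inputs from the SAP (Power and Sample Size): day-28 risks 0.13 and 0.065, one-sided alpha 0.05, power 0.80, 488 participants extended to 500.

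- Exponential hazard ratio: ln(1 - 0.065)/ln(1 - 0.13) = 0.4826.
- Schoenfeld events: 4(1.645 + 0.842)²/(ln 0.4826)² = 46.6.
- Total: 46.6/0.0975 = 478, within about 2% of the stated 488.

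The same method comes within 3% of every cell of SAP Table 1, so it is a fair basis for the next step.

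**Effect of retained cases.** Let q be the share of each arm already infected, kept in and counted as an event. The documents give no q; the values below are assumptions.

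- Arm risk: q + (1 - q)p.
- Risk difference: (1 - q)(0.13 - 0.065).
- Power at N = 500: Φ(½√D·|ln HR| - 1.645), with D = 500 × mean risk and HR recomputed from the two risks. This is a single-look calculation.

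| q | Control risk | HCIP risk | Risk difference | Risk ratio | Power, retained | Power, excluded |
|---|---|---|---|---|---|---|
| 0 | 0.1300 | 0.0650 | 0.0650 | 0.50 | 81.6% | 81.6% |
| 0.5% | 0.1344 | 0.0697 | 0.0647 | 0.52 | 79.6% | 81.4% |
| 1% | 0.1387 | 0.0744 | 0.0644 | 0.54 | 77.6% | 81.2% |
| 2% | 0.1474 | 0.0837 | 0.0637 | 0.57 | 73.9% | 80.9% |

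Worked line for q = 1%: control 0.01 + 0.99 × 0.13 = 0.1387; HCIP 0.01 + 0.99 × 0.065 = 0.0744; HR 0.517; D = 53.3; power Φ(2.404 - 1.645) = 77.6%. In the last column D = 500(1 - q) × 0.0975 and the hazard ratio stays at 0.4826.

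A risk-difference z-test with unpooled variance and 250 per arm gives 79.4% at q = 0, then 77.6%, 75.8% and 72.4%. The loss is about 2, 4 and 7 to 8 points by either method.

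**If the 13% already includes the prevalent cases.** The control risk among those not yet infected is then (0.13 - q)/(1 - q), and this is halved by treatment. Retained against excluded power is 74.5% against 78.5% at q = 1%, and 66.7% against 75.1% at q = 2%. Absolute power is lower, but the part due to the exclusion rule is again about 4 and 8 points.

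**The case against.** The strongest reply is that the entry rules nearly close the gap. A Day -1 swab known to be positive bars randomisation, and a negative validated test is needed within the 24 hours before infusion. That stands, and it limits the point to discordant, late-read specimens. A reader might infer that every infection present at screening stays in the analysis; the documents do not support that.

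The separate late-read swab is itself partly an inference. The Schedule of Events shows two molecular rows at screening, but the section 6 procedures list one pre-infusion test, which can be skipped if usual care supplied one that day. If a single specimen serves both purposes, the situation cannot arise. This affects how often it happens, not what the rule says when it does.

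Nor do the documents say that a baseline positive counts as an event. The endpoint is development of disease during follow-up, so the case might enter only through a later positive swab. That stands too, and the power figures are conditional on counting it.

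Sensitivity analysis 5 in the SAP drops events from transfusion to three calendar days afterwards. It would catch a prevalent case first counted at the Day 1 swab. It is a partial safeguard only: it is not the primary analysis and does not name positives from before transfusion.

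Finally, the move in the risk ratio from 0.50 to as much as 0.57 overstates attenuation on the planned scale. The SAP compares the risk difference and restricted mean survival time, and the risk difference shrinks only by the factor (1 - q).

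**Conclusion.** The point holds in a narrow form. The rule treats the same baseline finding differently according to the calendar date of the specimen, and no analysis in the SAP names the Day -1 case. A reader might infer a biased test or a false-positive risk. The documents do not support that: a screening specimen predates randomisation, so the affected share is expected to be equal in the two arms, and type I error is not inflated.

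The consequence is inconsistent handling, mild attenuation and some lost power, of the size tabulated above. The figures rest on an assumed q, on retained cases being counted as events, and on plasma not altering the status of someone already positive. They are illustrative for a further reason: the 13% and 6.5% are stated for symptomatic disease, while the primary endpoint is any molecular positive. The change is worth making because it is cheap, not because the damage is shown to be large.

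**What to change.** Replace the calendar-day rule in the SAP's Primary Analysis section. The primary analysis would exclude anyone with a positive molecular result, research or clinical, on any specimen collected from screening (Day -1) up to the start of transfusion, including results read later.

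Anchoring to the start of transfusion also settles the reverse case. The Day 1 visit has a window of one day either way, so a swab taken after the infusion could carry the transfusion date and be removed under the present wording.

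The cost is one sentence in the SAP and a few fewer analysed participants: at q = 1%, 495 instead of 500, with Schoenfeld power 81.2% against 81.6% if there were no such cases. Plasma cannot affect a specimen collected before it is given, so the exclusion favours neither arm.
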